### **Potential harms, discomforts and inconveniences to subjects**

Participants and parents may experience negative emotions when completing the study measures, which inquire about difficult thoughts or feelings that the participant may be experiencing. However, as all children referred to the study have presented to the ED with suicidal ideation or suicide-risk behaviours, children and families will encounter similar questions during their clinical assessment. There are no harms associated with the suicide prevention intervention. There were no adverse effects of the pilot of the intervention. The intervention is two hours per week and may present a significant commitment of time for the family.

Questionnaires that measure potential immediate risk, such as suicidal ideation, will be administered in person to the patient. They will be reviewed at the time of completion. If there is any indication of immediate safety risk the research staff member will alert the appropriate staff – either the study clinician administering the suicide intervention, or the treating physician, and will follow the suicide risk standard operating procedure that we have developed.

### **Adverse Event Reporting**

There are no expected adverse events related to the focused prevention suicide strategy or enhanced usual care. All expected and unexpected adverse events that occur during the participants' enrollment will be documented and reported as per Sickkids policy.

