In total there are four study visits. Participants will be assessed once by the study nurse at screening (the time of presentation in the ED), once by the study coordinator at baseline, and twice by the research assistant at 6 weeks post-randomization (at post-intervention), and 24 weeks post-randomization. Please see Table 1 for a complete measure administration schedule.

**Treatment allocation (F-SPS+UC or EUC):** Participants will be randomized to either receive the intervention, in addition to usual care (F-SPS+UC), or EUC only. They will be assigned in a 1:1 ratio of F-SPS+UC to EUC.

We will audio record F-SPS sessions if both the youth and the parent(s) or caregiver consent. These sessions will be reviewed by the principal investigators and the study staff in order to ensure fidelity to the treatment model.

In order to determine whether F-SPS+UC or EUC is related to a patient's health care service use, an analysis of participants' emergency room visits and unexpected medical appointments will also be conducted. OHIP numbers will be obtained at consent to link to ICES databases. .

We will recruit 128 adolescents to be randomized (64 adolescents per treatment arm) for this study (see 4.3 "Power Analysis").

**Intervention: F-SPS + UC (i)** is a manualized program that addresses the most common thoughts, feelings and conflicts that suicidal youth experience and teaches coping and safety skills to adolescents and their families. The program is the result of 3-years of development and quality improvement led by the PI ([name]), developed collaboratively with youth, families, and therapists. The program will be administered once weekly over 6 weeks by a trained therapist on an outpatient basis. Sessions consist of 1-hour spent one-to-one with the youth, followed by 1-hour with the youth and parent(s) or caregiver.

The therapist provides the youth and parent(s) or caregiver with a manual to use both during and between sessions. The program and manual address sources of conflict, ways to improve communication and ensure safety. The program resembles the only ED-based adolescent and family programs that have demonstrated effectiveness in decreasing suicidality. It is tailored to address the key concerns of the adolescent or family including mental health, academic problems, social or family conflict, acculturation issues, gender concerns or other stressors.

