Participants will also have access to the UC recommended by the ED circle of care. The F-SPS program will not interfere with the youth's ongoing plan of care. The F-SPS therapist will communicate with the youth's UC provider following the completion of the intervention, and provide detailed information about the intervention to the UC provider. This communication ensures that the UC provider is also informed about the challenges and strategies for the participant, so that the UC therapist is better able to assist the participant should similar situations reoccur in the future.

**Comparator: Enhanced Usual Care.** The comparator arm consists of weekly telephone checks for six weeks following the ED visit in addition to the UC recommended by the ED circle of care. The study coordinator will also contact parents in the comparator arm by telephone once weekly for six weeks. They will review changes to the youth's usual care and their contact with community resources in the 7 days prior to the phone call. As such, the aim of the EUC comparator is to improve access to mental health resources. It is not a therapeutic intervention in and of itself. The study coordinator will provide further information regarding community mental health resources as needed. If the parent indicates that the youth is in immediate risk for suicidal behaviour, 911 will be called. The ED team's referral suggestions plus weekly telephone follow-up represents EUC.

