### **Potential benefit to subjects and society**

Patients may benefit from participating in the intervention by accessing a suicide prevention program in addition to their treatment as usual. They are also assessed during at least two study time points for any immediate risk of self-harm, and an appropriate intervention can be applied if required.

There is currently no provincial or national strategy for preventing suicide attempts in Canadian adolescents. This study examines the effectiveness of one potential strategy that could be used as a foundation for creating such a strategy.

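### Spontaneously reported adverse events cannot be compared fairly between arms: no visit or measure asks about them, and the chance of hearing of them differs in weeks 1-6

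*Protocol*

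**What the plan says.** Under Potential harms, discomforts and inconveniences to subjects, the protocol states "There are no harms associated with the suicide prevention intervention", followed by "There were no adverse effects of the pilot of the intervention". The Feasibility paragraph calls the pilot open and does not give its size. Under Adverse Event Reporting it adds "There are no expected adverse events related to the focused prevention suicide strategy or enhanced usual care", and then makes a full commitment: "All expected and unexpected adverse events that occur during the participants' enrollment will be documented and reported as per Sickkids policy".

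Contact in the first six weeks is set out under Procedure. For F-SPS, "The program will be administered once weekly over 6 weeks by a trained therapist on an outpatient basis", and "Sessions consist of 1-hour spent one-to-one with the youth, followed by 1-hour with the youth and parent(s) or caregiver". For EUC there are weekly telephone checks, and "The study coordinator will also contact parents in the comparator arm by telephone once weekly for six weeks". The described content of those calls is changes in usual care and contact with community resources over the past 7 days. The therapist who runs the sessions and the coordinator who makes the calls both know the allocation.

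The same section has a blinded research assistant give the outcome measures at weeks 6 and 24 in both arms. It also provides for linkage to ICES databases.

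**The concern.** A promise to document every event needs a point at which someone asks. Without one, events come to light only if a participant or parent volunteers them, and that depends on how much contact there is, with whom, and about what. These differ by arm during treatment.

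At the same true event rate, more events would probably be heard of in F-SPS. A raw table by arm could then make F-SPS look harmful, or conceal a real reduction. A statement at the end that no adverse events occurred would be weak for a different reason, since nobody had asked. The trial is meant to decide whether F-SPS goes on to a larger multi-centre study, and that decision needs a usable account of harm. Declaring harm absent beforehand closes a question that the randomised comparison should leave open.

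**Working it through.** The protocol gives no figure on event ascertainment to reproduce. The sample size of 128 is not at issue here. The check compares what is promised with what is scheduled.

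**1. Is there an enquiry about adverse events?** Table 1 has no such row. No instrument under Measures is described as asking about adverse events. The Usual Care Tracking Survey, given weekly in both arms, records changes in care, so self-harm that led to no care falls outside it. The week-6 feedback forms might catch a volunteered complaint, but they are described only as soliciting feedback. The hospital policy is cited for documenting and reporting. The protocol itself names no visit, question, assessor or time window.

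**2. Contact in weeks 1-6.**
- F-SPS: 6 sessions x 2 h = 12 h with the youth, of which 6 x 1 h = 6 h is one-to-one.
- EUC: 6 calls x L, where the call length L is not stated. Assumed values: L = 5 min gives 0.5 h (the length of the tracking survey alone), 15 min gives 1.5 h and 30 min gives 3 h.
- The number of weekly contacts is the same, 6 against 6. What differs is duration, mode (in person or telephone) and the main informant (youth or parent).

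**3. Weeks 6-24.** 24 - 6 = 18 weeks with no arm-specific contact planned. Events may be lost here, but the schedule favours neither arm.

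**4. What the balanced sources cover.**
- SIQ-Jr, weeks 6 and 24, blinded and in person: ideation, not events.
- SBQ-R, same visits: suicidal behaviour over 1 month at follow-up. Taking a month as about 4 weeks, the two visits cover about weeks 2-6 and 20-24, which is 4 + 4 = 8 of 24 weeks. The gap between them is 20 - 6 = 14 weeks, and 14/24 = 58%.
- YSR and CBCL look back only 2 weeks at follow-up.
- ICES records, the health and social services diary and the week-24 Health Care Utilization Survey cover events that led to use of care, in both arms.

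Self-harm that led to no health-care visit between about weeks 6 and 20 therefore has no scheduled capture in either arm. In roughly the first two weeks it also lies outside the SBQ-R window, and only the unequal weekly contacts could reveal it.

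**5. Status of foreseeable events.** The Narrative Summary describes repeat ED visits for suicidal behaviour as common under usual care, and the second hypothesis counts acute crises as an outcome. The protocol does not say whether an attempt or a crisis visit is also recorded as an adverse event.

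**The case against.** The strongest reply is that the harms that matter most here are already measured even-handedly. Worsening ideation and suicidal behaviour are assessed by a blinded assessor on the same dates in both arms, and ED visits come from administrative records that do not depend on study contact. The section on potential benefit also says participants are "assessed during at least two study time points for any immediate risk of self-harm". This stands. A reader might infer that the trial can give no fair comparison of harms at all, and the documents do not support that.

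Other stronger readings also fail:
- *Contact of 12 h against 0.5 h.* The 0.5 h counts only a survey that both arms receive. Call length is not given. The calls also review care and supply resources, and the rule for a parent who reports immediate risk shows that they can bring out risk in the youth. The wording also leaves room for contact with the youth.
- *A numerical inflation of the event ratio.* It would need detection rates by arm, and the documents give none.
- *The week 6-24 gap as a source of bias.* It is the same in both arms, so it is incompleteness.
- *Attempts and crises treated as unforeseen.* The sentence on expected events concerns those related to the two interventions, and the next sentence commits to recording all events.

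It is also fair to say that the hospital policy is not shown and may prescribe an enquiry, and that tabulation by arm may sit in a statistical analysis plan. Neither removes the gap in the schedule that the protocol itself fixes.

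**Conclusion.** The point holds for spontaneously reported events. As the schedule stands they should not be compared by arm, because no common enquiry is set out and the opportunity to hear of them in weeks 1-6 is unequal: 12 h with the youth against six calls of unknown length, mainly with parents. The likely direction is more events heard of in F-SPS. That is an inference from the contact pattern, and its size cannot be estimated from the documents.

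The scheduled SIQ-Jr and SBQ-R and the health-care data give a balanced but partial view. The main hole is about 14 of 24 weeks for self-harm without a health-care visit, equal in both arms, on the reading that the 1-month recall is about 4 weeks. The flat statement of no harms goes beyond its only cited support, an open pilot. None of this threatens the primary analysis. It is a worthwhile and cheap improvement.

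**What to change.** 1. At the existing week-6 and week-24 visits, have the blinded research assistant ask youth and parent, in both arms, the same short set of closed adverse-event questions about the time since the last visit. The two windows, 6 + 18 weeks, cover the whole 24. Word the questions so that they do not prompt disclosure of treatment. Base any comparison by arm on these answers plus ICES data. List events heard in sessions or calls separately, with their source.

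2. Replace the statement that the intervention has no harms with one that no adverse effects were seen in the pilot. State that suicide attempt, self-harm, psychiatric admission, crisis ED visit and death are recorded in both arms as adverse events, as well as counted as outcomes where applicable.

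The cost is a protocol amendment, one short form and a few minutes at each of two visits. Parent outcome measures are REDCap surveys, so the parent's availability at the visit needs arranging. The recorded event count will be higher than under passive reporting. Recall over 18 weeks will lose some minor events, though on the same schedule in both arms. There is a small risk that an answer unblinds the assessor; closed questions, asked after SIQ-Jr and SBQ-R are complete, limit it.

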### **Potential benefit to subjects and society**

Patients may benefit from participating in the intervention by accessing a suicide prevention program in addition to their treatment as usual. They are also assessed during at least two study time points for any immediate risk of self-harm, and an appropriate intervention can be applied if required.

There is currently no provincial or national strategy for preventing suicide attempts in Canadian adolescents. This study examines the effectiveness of one potential strategy that could be used as a foundation for creating such a strategy.

### **Participant Withdrawal Criteria**

Participants and/or parents or guardians have the right to withdraw from the study at any time for any reason. The investigator also has the right to withdraw participants from the study if it is in the best interest of the participant. Should a participant and/or parent or guardian decide to withdraw, efforts will be made to document the reason for the withdrawal, if provided.

Participant withdrawal criteria are as follows:

- Withdrawal of informed consent (participant's decision to withdraw for any reason)
- Serious adverse event which, in the opinion of the investigator, indicates that continued participation in the study is not in the best interest of the participant
- Participant or parent or guardian non-compliance

In the event a subject is withdrawn due to an AE, this will be documented and participants will continue to be followed until these events are resolved or stabilized, if possible.

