This study will examine the effectiveness of a previously-piloted, ED-based suicide prevention intervention using a randomized clinical trial design. We will determine whether our patient- and Family-centered Suicide Prevention Strategy added to usual care (F-SPS + UC) is more effective than enhanced usual care (EUC) in reducing suicide-related behaviors in 128 youth at high-risk of suicide. F-SPS is a 6-week, outpatient program that teaches participants to identify and challenge the thoughts, feelings and conflicts that suicidal youth experience, and teaches them skills to manage impulses effectively. Piloting by the SickKids team has established the feasibility and acceptability of the intervention. Enhanced usual care consists of 6 weekly telephone calls to ensure that the participant has connected with community resources suggested by the ED team and provide additional resources as needed. Rigorous evaluation will investigate the intervention for an effect on suicide-related behavior and mental health crises (primary outcomes), mental health symptoms, patient/family functioning, economic costs, scale up/implementation feasibility and intervention fidelity (secondary outcomes). The proposed study is novel, in that it is the **first clinical trial of a youth suicide intervention in Canada**; it is efficient, in that it leverages the research-base and therapeutic infrastructure of a highly experienced child health team; and it is important, in that it targets the prevention of recurrent suicide attempts and of suicide, a leading cause of death. This study will be the first step toward developing an effective suicide prevention program that can be scaled-up and implemented across Ontario and Canada, to provide youth at high risk of suicide access to effective, evidence-based treatment, regardless of the community in which they live.

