#### **Measures:**

##### ***Primary Outcome Measures: Completed by Patient***

The **Suicide Ideation Questionnaire Junior High School Version (SIQ-Jr)** is a 15-item measure self-report of suicide ideation (e.g., thoughts about death and dying) completed by the patient. Items are scored from 0 to 6. The measure takes 5 minutes, and is completed in-person at baseline, week 6 and week 24.

The **Suicide Behavior Questionnaire – Revised (SBQ-R)** is a 4-item self-report questionnaire that measures suicide behaviour (i.e., previous suicide attempts or the likelihood of future attempts) over the

lifetime (at baseline) or over 1 month period (follow-up). The measure takes less than 5 minutes, and is completed in-person at baseline, week 6 and week 24.

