### **Power Analysis and Data Analytic Plan**

The sample size calculation is based on the assessment of between-group difference in change in SIQ-Jr score. This is a superiority study in which the implementation of the F-SPS intervention should only be recommended for study in a larger, multi-centre sample if the change in the primary outcome is significantly greater than in the control group. Two controlled clinical trials of an ED based intervention for suicidal youth have reported effect sizes of 0.4 for suicide attempt and 0.95 for suicidal ideation as measured by the SIQ-JR^23. A sample size of 128 participants provides 80% power ( $p=0.05$ ; 2-tailed t-test) to detect an effect size  $\geq 0.5$ , (based on a standard deviation [SD] of 14 and smallest clinically important difference of 7).

The principle of intent-to-treat will be applied to the analysis of outcomes. *H1*: The primary outcome SIQ-Jr will be compared between arms using repeated measures ANOCOVA with the corresponding baseline measure as the covariate. Mean differences and corresponding confidence intervals will be calculated. A two-sided, p-level of 0.05 will be applied for the primary outcome. *H2*: The number of unscheduled hospital visits will be compared between arms using a Poisson model. The two-sided level for the secondary outcomes will be adjusted (Bonferroni) to account for multiple testing. Implementation outcomes (i.e., fidelity to the intervention protocols) will inform client outcomes. Analysis of implementation data will be descriptive (fidelity to implementation of F-SPS model in both sites), and associative (statistical association of clinician fidelity to F-SPS and patient outcomes).

**Feasibility.** The ED at SickKids manages more adolescents with acute mental health presentations than any other hospital in the Toronto Central LHIN (TC-LHIN), on average 842 per year, (we estimate more than half for SRB). Sick Kids also has a strong history of successfully conducting ED-based RCTs and has

an established research infrastructure for identification and recruitment of potential research participants (Pediatric Research Academic Initiative at SickKids Emergency [PRAISE]). In addition, through our previous development work including an open pilot in the Urgent Care (Crisis) Clinic, several therapists at our centre are familiar with the intervention and have experience using it with acutely suicidal youth and families.

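### Undefined non-compliance is a ground for withdrawal from the study, with no statement that SIQ-Jr follow-up continues, so it may weaken the intent-to-treat analysis

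*Protocol*

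**What the plan says.** The Participant Withdrawal Criteria speak of withdrawal from the study as a whole and list three grounds: withdrawn consent, a serious adverse event that in the investigator's opinion makes continuing inadvisable, and "Participant or parent or guardian non-compliance". The protocol does not say what the non-compliance is with, how much of it counts, or who decides. It has no category for a participant who stops sessions or calls but stays in follow-up. The one statement about follow-up after withdrawal concerns safety: "In the event a subject is withdrawn due to an AE, this will be documented and participants will continue to be followed", until the event resolves or stabilises.

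The Power Analysis and Data Analytic Plan says: "The principle of intent-to-treat will be applied to the analysis of outcomes". The primary analysis is a repeated-measures analysis of covariance of SIQ-Jr with baseline as covariate. Of the SIQ-Jr, the Measures section says: "Items are scored from 0 to 6. The measure takes 5 minutes, and is completed in-person at baseline, week 6 and week 24".

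On what each arm asks of families, the protocol says of F-SPS: "The program will be administered once weekly over 6 weeks by a trained therapist on an outpatient basis", and of enhanced usual care (EUC): "The study coordinator will also contact parents in the comparator arm by telephone once weekly for six weeks". The section on harms and inconveniences adds: "The intervention is two hours per week and may present a significant commitment of time for the family". The Narrative Summary states: "Piloting by the SickKids team has established the feasibility and acceptability of the intervention".

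The Procedure section has the coordinator book the week-6 and week-24 visits in advance, timed from randomisation, and allows them at the hospital or at home.

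**The concern.** Compliance is observed after randomisation. An intent-to-treat comparison is meant to keep participants who do not take up their assigned programme. A criterion that lets non-compliance end study participation can take those same participants out of the primary outcome. Unlike withdrawal of consent, it can be used while the family is still willing to be assessed, so the loss would be avoidable.

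SIQ-Jr is collected in person, and scores that were never collected cannot be recovered at analysis. Any later handling would rest on assumptions about the participants withdrawn. If withdrawal differs by arm, and those withdrawn differ in outcome from those retained, the primary comparison is biased. The arms do ask for different commitments, so a difference is plausible, but the protocol gives neither its direction nor its size.

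**Working it through.** **Timing under the two readings of the term**

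- *Missed sessions or calls.* These run over weeks 1 to 6 (Procedure; Table 1), and the first post-randomisation SIQ-Jr is at week 6. Withdrawal on this ground would probably come before or about that visit. The participant may then contribute no post-randomisation score to the repeated-measures model.
- *Missed assessments.* The missed score is lost whatever the rule says. The rule costs only a later score, for example week 24 after a missed week 6.

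**Inputs from the protocol.** 128 participants, 64 per arm; SD 14; difference 7; two-sided 0.05; 80% power. These reproduce: a two-sample t-test at effect size 7/14 = 0.5 needs 63.8, so 64 per arm, and gives 80.1% power.

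**Assumed inputs (none in the protocol).** A share pF of the F-SPS arm and pE of the EUC arm is withdrawn with no SIQ-Jr score. Those withdrawn score 7 points worse on average than those retained. The baseline correlation is 0.5. One time point is analysed.

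**Formulas**

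- In each arm the retained mean looks better than the full-arm mean by p × gap, so bias in favour of F-SPS = gap × (pF − pE).
- SE = SD × √[1/(64(1 − pF)) + 1/(64(1 − pE))].
- False-positive rate = P(|Z + bias/SE| > 1.96).
- Baseline-adjusted SD = 14 × √(1 − 0.5²) = 12.12.

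**Results with pF = 20%**

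| EUC loss | Unadjusted, gap 7 | Adjusted, gap 7 remains | Adjusted, gap 3.5 remains |
|---|---|---|---|
| 20% | bias 0; 5.0% | bias 0; 5.0% | bias 0; 5.0% |
| 10% | bias 0.7, SE 2.689; 5.8% | bias 0.7, SE 2.329; 6.0% | bias 0.35, SE 2.329; 5.3% |
| 0% | bias 1.4, SE 2.625; 8.3% | bias 1.4, SE 2.273; 9.4% | bias 0.7, SE 2.273; 6.1% |

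Worked cell (adjusted, gap 7, EUC loss 10%): bias = 7 × (0.20 − 0.10) = 0.7; SE = 12.12 × √(1/51.2 + 1/57.6) = 2.329; bias/SE = 0.30; rate 6.0%. A simulated analysis of covariance (20,000 trials, gap 7 remaining) gave 5.2%, 6.0% and 9.2% for the three rows.

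**Sensitivity**

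- Smaller losses, adjusted: 10% against 5% gives 5.3% (gap 7) or 5.1% (gap 3.5); 10% against none gives 6.2% or 5.3%.
- Other correlations, gap 7 remaining: at 0.3 the rates are 5.9% (20% against 10%) and about 8.7% (20% against none); at 0.7 they are 6.5% and 11.6%.
- Reverse direction: if those withdrawn do 7 points better, the bias has the same size against F-SPS. A true 7-point benefit would be estimated as 7 − 0.7 = 6.3 or 7 − 1.4 = 5.6 points.

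**The case against.** Five points can be made in the protocol's favour.

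1. *No contradiction.* Grounds for withdrawal and an analysis principle can stand in one protocol. A reader might infer that the two sections conflict; they do not. What stands is that the withdrawal rule, read one way, may deprive the analysis of the data it needs.
2. *Nothing says that scores stop.* A reader might infer that withdrawal for non-compliance ends SIQ-Jr collection. The text does not say so, and it does not say that the criterion must be used or that it means missed sessions. Visits are timed from randomisation rather than attendance, may be at home, and are done by a blinded research assistant. This lowers the risk. It still leaves open what happens once a participant has been formally withdrawn from the study.
3. *Differential loss is conjecture.* A reader might infer that F-SPS will lose more families because it takes two hours a week. The protocol also reports that piloting established feasibility and acceptability, and EUC families can miss calls too. Only the possibility stands.
4. *The sizes are assumed and mostly small.* This stands in full.
5. *Missing data belong to the statistical analysis plan.* This is right for their handling, and no fault is found there. Collection is settled by the protocol, and no analysis plan can supply scores that were not taken.

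Nor is the health-service linkage for unscheduled visits at issue: nothing says that withdrawal ends it.

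**Conclusion.** The concern holds in conditional form. Non-compliance is a stated but undefined ground for leaving the study, and the protocol does not say that outcome assessments continue afterwards. If the ground is applied to missed sessions or calls, it may cost the week-6 and week-24 SIQ-Jr scores of randomised participants and so may weaken the intent-to-treat analysis. If it means missed assessments, much less is lost.

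Bias needs two further conditions: withdrawal that differs by arm, and an outcome difference between those withdrawn and those retained. With equal loss and the same gap there is none. The illustrative baseline-adjusted false-positive rate is about 5.3% to 6.0% with losses of 20% against 10%, and about 6% to 9% with 20% against none. These ranges rest on the assumed 7-point gap, half or all of it left after adjustment, and a correlation of 0.5; they are not estimates for this trial. The bias could equally run against F-SPS. The change is worth making because it is cheap and the loss could not be repaired later, not because a large effect has been shown.

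**What to change.** Amend the Participant Withdrawal Criteria to state three things:

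- Non-compliance with the assigned sessions or calls does not by itself end study follow-up.
- Such participants are still asked for the week-6 and week-24 assessments unless consent for data collection is withdrawn.
- A missed week-6 assessment does not cancel the week-24 request.

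Decisions on stopping the intervention and on safety withdrawal stay with the investigators; the wording sets no threshold for either.

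The cost is a few sentences and the contact effort for two visits already scheduled, with no extra participants. Recovery will be incomplete because some families who have stopped will decline, and less is gained if the term was meant to cover missed assessments.
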